## 8. Study Population

8.1. Inclusion Criteria: In order to be eligible to participate in this study, an individual must meet all of the following criteria:

### Experimental Group:

1. Male or female of at least 3 years and <18 years of age at screening.
2. Written informed consent from participant's legal representative and assent (when applicable) obtained from participant and ability for participant to comply with the requirements of the study.
3. Stated willingness to comply with all study procedures and availability for the duration of the study
4. Be scheduled for and receive a liver transplant or total pancreatectomy and islet cell autotransplantation

### Control Group:

1. Male or female of at least 3 years and <18 years of age at transplantation.
2. Received a liver transplant or total pancreatectomy and islet cell autotransplantation.

8.2. Exclusion Criteria: An individual who meets any of the following criteria will be excluded from participation in this study:

### Experimental Group:

1. Pregnant or unwilling to abstain from sex if not practicing birth control during participation in the study.
2. Presence of a condition or abnormality that in the opinion of the Investigator would compromise the safety of the patient or the quality of the data.

## MEDICAL PROTOCOL (HRP-590)

PROTOCOL TITLE: Magnesium sulfate as adjuvant analgesia and its effect on opiate use by post-operative transplant patients in the pediatric ICU.

VERSION DATE: 06/09/2022

3. Known allergic reactions to components of the MgSO4
4. History of heart block or myasthenia gravis in past medical history.
5. Presence of cardiac pacemaker.
6. Age less than 3 years or greater than 18 years at screening.
7. Any patient with preoperative creatinine level > 1.5x upper limit of normal.
8. If study staff member not available for in-hospital presence on day of procedure.

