### 5. Procedures Involved

#### 5.1. Study Design:

Experimental Group: Prospective Cohort of next 30 incoming liver and TPIAT transplant children which meet inclusion criteria. Due to the more difficult predictability of when liver transplants occur, and to ensure adequate enrollment of 30 patients occurs within the 3-year pilot duration, we have chosen not to have a 50/50 balanced prospective cohort.

Control Group: Control will be via retrospective chart review of the last 60 transplant patients from the same population (liver, TPIAT) with same surgeon. Intervention and data collection will be as outlined elsewhere in protocol.

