### Control Group:

1. Any patient who had filed as research-exempt (opt-out of research previously).
2. Age less than 3 years or greater than 18 years at transplantation.
3. Any patient with preoperative creatinine level > 1.5x upper limit of normal.

8.3. Screening: No specific screening measures will be used. Any transplant patient will be considered eligible if not pregnant. All consent/recruitment for the study is at same time as transplant procedural consent, which is performed by the transplant surgeon (whom is also a Co-Investigator on this study).

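### Most prospective exclusions, including staff availability, are not applied to the historical controls, so hard-to-schedule liver cases may be under-represented in the magnesium group, and urgency is neither recorded nor adjusted for

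*Combined protocol and SAP*

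**What the plan says.** **Control source.** Section 5.1: "Control will be via retrospective chart review of the last 60 transplant patients from the same population (liver, TPIAT) with same surgeon".

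**Exclusions in section 8.2.** The prospective list has eight items. Two also appear in the control list: the age limits, and "Any patient with preoperative creatinine level > 1.5x upper limit of normal". The other six apply to prospective patients only:
- "Pregnant or unwilling to abstain from sex if not practicing birth control during participation in the study"
- a condition that "in the opinion of the Investigator would compromise the safety of the patient or the quality of the data"
- known allergy to components of the study drug
- "History of heart block or myasthenia gravis in past medical history"
- a cardiac pacemaker
- "If study staff member not available for in-hospital presence on day of procedure"

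The one control-only exclusion is "Any patient who had filed as research-exempt (opt-out of research previously").

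**How the staff rule works.** Under section 18.1, a patient for whom no staff member is expected to be available is not consented, and a patient is taken out of the study if staff become unavailable on the day. Section 12.1 lists the same situation as a ground for ending participation.

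**Consent.** Prospective patients need consent, and section 9.2 excludes families who, under stress, do not want to discuss the research. Section 21.2 seeks a waiver of consent for controls.

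**Urgent cases.** Sections 9.2, 11.1 and 21.1 foresee acute or emergent liver transplants and give a consent route for them. Section 5.1 explains the unbalanced prospective cohort this way: "Due to the more difficult predictability of when liver transplants occur".

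**Data and model.** The section 15.1 list contains no urgency, planned/unplanned or surgery start-time field. The adjusted model in section 15.3 uses transplant type, age and gender. Section 19.1 says comorbidities and transplant indication will not be identified in either group.

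**The concern.** With historical controls, nothing but the selection rules and the covariates makes the groups comparable. Here one group passes through filters that the other does not.

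The filter most likely to matter is staff availability. A study member has to be in the hospital on the day and visit the operating room every two hours (section 18.1). That is easiest to arrange for a scheduled operation and hardest for one called at short notice. In this protocol the short-notice operations are liver transplants. The stress-related consent exclusion acts on the same patients and in the same direction.

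If liver cases operated on urgently need more or less opioid than planned ones, a different mix of the two would appear as a magnesium effect, or mask one. Transplant type in the model does not remove a difference within liver transplants, and without an urgency field nobody could see afterwards whether it had occurred. Section 15.3 makes this the primary comparison, judged at the two-sided 5% level, so the pilot label does not make it harmless.

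**Working it through.** **1. The plan's own figure.** Inputs from section 15.2: SD 8.3 mg/kg, 80% power, and two-sided 5% from section 15.3. With 90 per group the normal approximation gives 8.3 × √(2/90) × (1.960 + 0.842) = 3.47 mg/kg. The t-test version gives 3.49, which matches the table. I use 3.49 mg/kg as the yardstick.

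**2. The lists side by side (section 8.2).**

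| Rule | Prospective | Control |
|---|---|---|
| Age | yes | yes |
| Creatinine | yes | yes |
| Pregnancy/contraception | yes | no |
| Investigator judgement | yes | no |
| Study-drug allergy | yes | no |
| Heart block/myasthenia gravis | yes | no |
| Pacemaker | yes | no |
| Staff availability | yes | no |
| Research opt-out | no | yes |

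Six rules act on the prospective group alone. Most of the medical ones can be checked in a chart. Investigator judgement, willingness on contraception and staff availability cannot be reconstructed for a past patient.

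**3. Size of a shift, on assumptions.** Let f_c and f_m be the shares of urgent cases in controls and in the magnesium group, and D the difference in mean total opioid between urgent and planned cases. The unadjusted group difference moves by (f_c − f_m) × D. The documents give none of the three quantities. Assume f_c − f_m of 10-20% and D of 5-10 mg/kg (0.6-1.2 SD):
- low: 0.10 × 5 = 0.5 mg/kg; 0.5/3.49 = 14%
- high: 0.20 × 10 = 2.0 mg/kg; 2.0/3.49 = 57%

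Urgent cases are described only for liver. If f_m = 0, 10-20% of 60 controls is 6-12 patients, or 20-40% of the 30 liver controls. Any urgent cases enrolled prospectively shrink the shift.

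**4. After adjustment for transplant type.** The bias then acts only within the liver stratum, where it is 0.20 × 5 = 1.0 to 0.40 × 10 = 4.0 mg/kg. The pooled estimate weights each stratum by n₁n₂/(n₁+n₂), with 30 controls in each. The prospective split is not fixed, so I show three assumed splits:

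| Liver : TPIAT | Liver weight | Shift, mg/kg |
|---|---|---|
| 10 : 20 | 7.5/(7.5+12) = 38% | 0.38-1.54 |
| 15 : 15 | 10/20 = 50% | 0.5-2.0 |
| 20 : 10 | 12/19.5 = 62% | 0.62-2.46 |

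If liver is the minority, adjustment reduces the shift; it does not remove it.

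**5. Effect on the test.** With no true effect, 60 controls against 30 and SD 8.3 (unadjusted t-test), the chance of a significant result favouring magnesium is 2.5% without bias. It is about 4.5% with a shift of 0.5 mg/kg and about 19% with 2.0. If D is negative, the bias runs against magnesium.

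**6. Cost of trimming controls.** If matched exclusions removed 10-30% of controls without replacement (54 down to 42), power for 3.49 mg/kg would fall from 46% to 45-41%. A longer look-back avoids even that.

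**The case against.** A reader might infer that urgent cases are shut out of the magnesium group. The documents do not support that. No criterion excludes them, and sections 9.2, 11.1 and 21.1 plan for their enrolment. The most that can be said is that they may be under-represented.

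A reader might also infer that all medical exclusions are one-sided. They are not: the creatinine rule is the same for both groups, and age is shared.

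The link from staff absence to urgency is not stated anywhere. Section 5.1 says only that liver timing is hard to predict. Section 18.1 has the investigators notified of every planned transplant and a study member reachable at all times, and no rate of staff unavailability is given. Being reachable is not being in the hospital, however, so the inference stays plausible.

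Patients removed on the day need not vanish from the analysis. Section 12.2 keeps data already collected and intends to go on collecting, and section 15.3 promises intention to treat. The clear filter is therefore the one before consent. The plan does not say how a patient removed on the day is counted.

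The rare contraindications have no stated link to urgency or opioid use. Mirroring them serves consistency and probably changes little.

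Finally, sections 19.1 and 19.2 limit what is read from charts, and the controls are under a consent waiver. That is a real constraint on the wording of the fix. But section 19.1 concerns comorbidities and indication, not whether an operation was planned. Under section 5.2 control charts are already opened by surgical encounter and date.

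**Conclusion.** The point holds in this limited form. Six of the eight prospective exclusions, together with consent, filter the magnesium group alone, while section 5.1 calls the controls the same population. Under-representation of urgent or hard-to-schedule liver cases in the magnesium group is a plausible inference, not something the documents state. Because urgency is neither recorded nor modelled, such an imbalance would bias the primary comparison within liver transplants and could not be detected.

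Size and direction are unknown. The 0.5-2.0 mg/kg range (14-57% of 3.49) rests entirely on the assumed share and excess. It is smaller if urgent cases are also enrolled prospectively, or, after adjustment for type, if liver is the minority of that cohort. It would be wrong to conclude that the design favours magnesium: nothing in the documents says whether urgent cases use more opioid or less.

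This is a cheap improvement to a comparison that will remain non-randomised, not a reason to reject the design.

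**What to change.** - **Sections 8.2 and 5.2:** when selecting the 60 controls, apply the prospective exclusions that a chart can verify (heart block or myasthenia gravis, pacemaker, study-drug allergy, pregnancy), as is already done for creatinine. Extend the look-back if needed to keep 60.
- **Section 15.1:** add surgery start time and planned/urgent status for both groups, with one written definition.
- **Section 18.1:** log every prospective patient not approached, or removed, because of staff availability, with transplant type and planned/urgent status. Start now, since missed cases are hard to reconstruct later. State how patients removed on the day are counted under section 15.3.
- **Section 15.3:** pre-specify one sensitivity analysis of the primary outcome, either adjusted for urgency or restricted to planned cases.

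Leave the staff-presence safeguard unchanged.

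The cost is two more chart fields, a short log, one more model, and an eligibility check of control charts. That check must be written into the plan alongside the data-access limits in sections 19.1 and 19.2 and the waiver in section 21.2. The change does not make the groups exchangeable: investigator judgement and consent cannot be mirrored in controls, and the report should say so.

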### Control Group:

1. Any patient who had filed as research-exempt (opt-out of research previously).
2. Age less than 3 years or greater than 18 years at transplantation.
3. Any patient with preoperative creatinine level > 1.5x upper limit of normal.

8.3. Screening: No specific screening measures will be used. Any transplant patient will be considered eligible if not pregnant. All consent/recruitment for the study is at same time as transplant procedural consent, which is performed by the transplant surgeon (whom is also a Co-Investigator on this study).

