#### 5.2. Study Procedures:

Experimental Group: There will be no operative procedures per study parameters (though the transplantation procedure itself as well as any secondary procedures from complications are otherwise per standard of care). Patient's medical record will be reviewed for basic eligibility criteria (history of myasthenia gravis or heart block). If female and of reproductive age, patient will have a urine B-hCG, which is routine prior to any abdominal surgery. The only prospective study procedure will be the magnesium protocol previously outlined, where IV MgSO4 will be delivered as a 30-minute bolus dose of 50 mg/kg (maximum 2 grams) in OR followed by a 15 mg/kg/hr infusion initiated immediately after (i.e. in OR as well) until conclusion of PICU stay or 48 hours, whichever comes first. Magnesium levels will be monitored throughout the duration of the infusion per above - every 2 hours in OR starting after bolus dose, then every 4 hours [expected window +/- 1 hour]. There are no other baseline visits or follow-up visits independent of the PICU stay and initial consent process. We do not anticipate this study intervention impacting workflow significantly, as infusion medications are standard interventions in the PICU, and these patients already have frequent blood draws. A study schedule with these interventions will be created via OnCore program to ensure compliance with protocol. Data outcomes will be collected from epic EMR at the conclusion of each patient's ICU admission by co-investigator and medical student researcher and stored in REDCap. All collected data is via EMR, so no surveys/scripts/forms are needed for data collection. Specifically, the EMR will be accessed for appropriate transplant patient, followed by selecting the appropriate surgical encounter (which would be current), followed by selecting only specific portals in Epic EMR where intended data elements are located (for example: Intake/Output section, or results review -> magnesium level, etc). Only specific data collection pathways will be targeted while in a patient's medical chart. There are no other drugs/devices involved in study or that would alter MgSO4 delivery. Similarly, there are no out-of-hospital prescriptions or interference during the ICU admission which would alter the study protocol. Any out-of-hospital contact (i.e. pre-admission consent if performed) will include adherence to COVID precautions per hospital guidelines.

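### Section 8.3 makes any non-pregnant transplant patient eligible, contradicting the eight exclusions in 8.2, and no named pre-dose step covers creatinine, pacemaker or allergy

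*Combined protocol and SAP*

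**What the plan says.** Three sections of the protocol bear directly on who may enter the experimental group.

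- **8.2 Exclusion Criteria** is introduced as binding: "An individual who meets any of the following criteria will be excluded from participation in this study". Eight criteria follow for the experimental group. They include "Known allergic reactions to components of the MgSO4" (item 3), "History of heart block or myasthenia gravis in past medical history" (item 4), "Presence of cardiac pacemaker" (item 5) and "Any patient with preoperative creatinine level > 1.5x upper limit of normal" (item 7).
- **8.3 Screening** says "No specific screening measures will be used" and then "Any transplant patient will be considered eligible if not pregnant".
- **5.2 Study Procedures** describes a review of the medical record for "basic eligibility criteria (history of myasthenia gravis or heart block") and a urine pregnancy test for girls of reproductive age.

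Section 18.2 adds, as the first item in its list of safety data, a confirmation that the participant satisfied the inclusion and exclusion criteria. Section 12.1 lets an investigator end participation when an exclusion criterion is newly developed or was not recognised before.

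**The concern.** The section headed Screening is where site staff would look for the rule on whom to enrol. The rule there has a single bar, pregnancy. A non-pregnant child with a pacemaker is eligible under 8.3 and excluded under 8.2.

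The sections that describe what staff actually do before dosing do not make up the difference, because three exclusions that can be read from the chart are never named as something to check. What is at stake is the entry of a child whom the protocol's own list excludes, into a study of an investigational infusion given under an IND. The risk of a missed check is greatest when time is short, and sections 11.1 and 21.1 allow for liver transplants that arise acutely, with consent taken while the child is already an inpatient.

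**Working it through.** No arithmetic applies; this is a comparison of text. The table takes each experimental-group exclusion in 8.2 and asks whether 8.3, 5.2 or another section names a step for it before the first dose.

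| 8.2 item | In 8.3 | In 5.2 | Named elsewhere before dosing |
|---|---|---|---|
| 1. Pregnancy, or unwilling to abstain without birth control | Pregnancy only | Pregnancy test only | No |
| 2. Investigator's opinion | No | No | Discretionary; no check named |
| 3. Allergy to components | No | No | No |
| 4. Heart block or myasthenia gravis | No | Yes | No |
| 5. Pacemaker | No | No | No |
| 6. Age | No | No | Age limits also in 8.1 |
| 7. Preoperative creatinine | No | No | No |
| 8. Study staff present in hospital | No | No | Yes, 18.1 |

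**Step 1: 8.3 against 8.2.** 8.3 recognises part of one item out of eight. For the rest, its wording admits patients whom 8.2 rejects. This is a direct contradiction. There is a smaller inconsistency too: 8.1 and 8.2 fix age at screening, while 8.3 says there are no specific screening measures.

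**Step 2: 5.2 against 8.2.** 5.2 names item 4 and the pregnancy part of item 1. It describes its list as basic and does not say that nothing else is checked, so it is incomplete rather than contradictory.

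**Step 3: what is left over.** Item 8 is put into operation in 18.1, which bars consent if no staff member is expected to be available and removes the patient if one becomes unavailable on the day. Item 6 repeats an inclusion limit. Item 2 is a judgement. Items 3, 5 and 7 (allergy, pacemaker, creatinine) are objective, can be checked in the chart, and have no named step.

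**Step 4: does 18.2 close the gap?** It covers every criterion, so in scope it does. In timing it does not. The item is worded in the past tense and sits among safety data collected from a baseline visit onward, while 5.2 says there are no baseline visits apart from the PICU stay and the initial consent process. Under 4.1 the bolus is given in the operating room, before the PICU stay. Nothing ties the confirmation to a point before that bolus.

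**The case against.** The best defence is that 8.1 and 8.2 are plainly meant to govern. 8.1 requires all its criteria to be met, 8.2 excludes on any one, and 9.2 refers back to the exclusion criteria as the operative list. On this view 8.3 is loose wording about screening tests; taken literally it would also cancel the age limits, which nobody intends. Several safeguards exist besides: the 18.2 confirmation, the team briefing in 18.1 before the infusion starts, the external monitor's review of eligibility determinations (18.1), and the annual report on whether participants met entry criteria (18.2).

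Much of this stands. The intent is probably that 8.2 binds, and the safeguards soften the gap. They do not close it. The briefing covers pertinent protocol elements without naming eligibility, the monitor works at regular intervals rather than for each patient before dosing, and the annual report looks back. If 8.2 is meant to bind, the sentence in 8.3 is simply wrong and should go.

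A reader might infer more than the documents support:

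- **That 5.2 contradicts 8.2.** It can be read as giving examples of basic criteria.
- **That the creatinine filter is unmatched between the groups.** The exclusion is worded identically for experimental and control patients, and the control procedure in 5.2 names no creatinine check either. An imbalance would arise only if staff applied 8.2 to controls and not to prospective patients.
- **That a wrongly enrolled child will be dosed and then withdrawn.** 12.1 is permissive and does not say that recognition follows dosing.
- **That the staff-presence exclusion is not implemented.** 18.1 implements it.

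**Conclusion.** The point holds as a contradiction between 8.3 and 8.2, together with an incomplete list in 5.2. Three objective safety exclusions (creatinine, pacemaker, allergy) have no named step before dosing, and the one general confirmation, in 18.2, has no pre-dose timing.

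The consequence is a possibility: read literally, 8.3 could admit a child whom 8.2 excludes. The documents give no figures from which to say how many, and no effect on the primary comparison has been shown. The conclusion assumes only that staff may act on the screening section as written; if they always work from 8.2, no wrongly enrolled child results and the defect is one of wording. Because the affected criteria concern safety and the correction is cheap, it should be made.

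**What to change.** Reconcile 5.2, 8.2, 8.3 and 18.2:

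1. In 8.3, replace the sentence declaring any non-pregnant transplant patient eligible with a reference to 8.1 and 8.2.
2. In 5.2, make the record review cover the criteria in 8.1 and 8.2 rather than two conditions.
3. In 18.2, require the confirmation of inclusion and exclusion criteria to be documented before the first dose of study drug, for every criterion that can be known by then.

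The timing should be before dosing rather than before consent. 8.1 includes consent itself, and consent may be taken at an outpatient visit when day-of-surgery facts are not yet known. Receipt of the transplant cannot always be confirmed even before dosing, since 4.1 places the TPIAT bolus just after induction of anaesthesia; hence the limit to what can be known beforehand.

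No eligibility threshold is proposed or changed. The cost is a few sentences and a short eligibility form with a line and date for each criterion. The documents do not say when the preoperative creatinine is measured, so the form should record the date of the value used.
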